### 10.6.1. Post-Administration Procedures

Following AVXS-101 administration patients will return to a designated PICU bed, or other appropriate setting, with close monitoring of vital signs. Concomitant medications and all AEs/serious adverse events (SAEs) will also be monitored and documented following dosing procedures.

Patients will be kept in the PICU patient room or other appropriate setting (e.g., interventional suite, operating room, dedicated procedure room) with immediate access to acute critical care management for 48 hours for closer monitoring of mental status. During the inpatient stay, personnel are required to follow appropriate safety precautions as per institutional standards for infection control; standards should require personal protective equipment (PPE) such as gowns, gloves, masks, glasses, and closed-toe shoes. Patients' families will be provided standardized, IRB-approved handouts regarding monitoring for mental status changes which includes

monitoring for severe headache, fever, irritability, neck pain or stiffness, light sensitivity, vomiting, and lethargy (tiredness). Patients may be discharged from the hospital when the following criteria are met:

- Afebrile
- Absence of hypersensitivity reactions
- Absence of meningismus
- Absence of abnormal laboratory values suggestive of possible CNS infection or complication

## 10.7. Dose Escalation

There will be a 4-week dosing interval between all patients within Cohort 1 to allow review of the safety analysis from six-time points (Days 1, 2, 7, 14, 21, 30) prior to dosing of the next patient.

AveXis will confer with the DSMB/DMC on all Grade III or higher AEs within approximately 48 hours of awareness that are possibly, probably or definitely related to the study agent before continuing enrollment. Safety data will be reviewed by the DSMB/DMC during quarterly meetings; following enrollment of the first three patients  $\geq 6$  months and  $< 24$  months of age at the time of dosing and based upon the available safety data a decision will be made whether to: a) stop due to toxicity, or b) proceed to Cohort 2 using Dose B.

Should the determination be made to advance to Cohort 2 (Dose B), again there will be at least a 4-week interval between dosing of the first three patients  $< 60$  months of age at the time of dosing within the cohort. Based on the available safety data from the first three Cohort 2 patients and all of the Cohort 1 patients, the DSMB/DMC may decide and document during quarterly meetings that further 4-week intervals between patients dosing is unnecessary. AveXis will take this recommendation into consideration and will make the final determination whether to persist with 4-week intervals between patients dosing going forward. The decision will be communicated to sites and IRBs in a formal sponsor letter. AveXis will confer with the DSMB/DMC on all Grade III or higher AEs within approximately 48 hours that are possibly, probably or definitely related to the study agent before continuing enrollment. Safety data will be reviewed by the DSMB/DMC during quarterly meetings; following enrollment of the first six patients and based upon available safety data, a decision will be made whether to a) stop due to toxicity or b) continue to enroll an additional 21 patients until 12 patients  $\geq 6$  months and  $< 24$  months of age at time of dosing and 12 patients  $> 24 < 60$  months of age at time of dosing have received Dose B.

Based upon an ongoing assessment of safety and efficacy data from patients treated with the  $1.2 \times 10^{14}$  vg dose, an option for testing of a third dose (Dose C), will be considered. If, based on all available data, this is judged to be safe and necessary, three patients  $< 60$  months of age will receive Dose C,  $2.4 \times 10^{14}$  vg administered IT. A meeting of the DSMB/DMC will be called to obtain a recommendation on the safety of escalating to a higher dose prior to proceeding. If a decision is made to proceed to testing a higher dose, there will again be a four-week interval between dosing of the first three patients receiving Dose C, as in Cohorts 1 and 2. Safety data will be reviewed by the DSMB/DMC during quarterly meetings. Following enrollment of the

first three Dose C patients and based upon available safety data, the DSMB/DMC will be consulted and a decision will be made whether to: a) stop dosing Dose C due to safety concern, or b) continue to enroll an additional 21 patients until there are a total of 12 patients  $\geq$ 6 months and  $<$  24 months and 12 patients  $\geq$  24 and  $<$  60 months that have received Dose C.

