## **7.5. Criteria for Study Termination**

An independent DSMB/DMC and medical monitor will monitor safety data on a continual basis throughout the trial. The DSMB/DMC can recommend early termination of the trial for reasons of safety. Study enrollment may be halted when any patient experiences a Grade III, or higher AE toxicity that is unanticipated and possibly, probably or definitely related to the study product that presents with clinical symptoms and requires medical treatment. This will include any patient death, important clinical laboratory finding or any severe local complication in the injected area related to administration of the study agent. If after review by the DSMB/DMC the decision is made to continue, the study will proceed according to the dose escalation schedule.

The trial may be terminated for the following reasons:

- Development of unacceptable toxicity, defined as the occurrence of any unanticipated Common Terminology for Adverse Events (CTCAE) Grade 3 or higher AE/toxicity that is possibly, probably, or definitely related to gene replacement therapy, and is associated with clinical symptoms and/or requires medical treatment
- DSMB/DMC can recommend early termination of the study for safety reasons
- Study is terminated by sponsor
- Regulatory Authority recommendation

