## 8. SELECTION AND WITHDRAWAL OF PATIENTS

Patients with a genetic diagnosis consistent with SMA, bi-allelic deletion of SMN1 and 3 copies of SMN2 without the genetic modifier who demonstrate the ability to sit unassisted for 10 or more seconds but cannot stand or walk at the time of study entry will be enrolled in this clinical trial. Patients will be of any racial, ethnic, or gender background. Enrollment will be staggered with at least four weeks between patient injections for all patients in Cohort 1 and at least the first three patients in Cohort 2 and Cohort 3.

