**Table 7: Total Blood Volume**

Visit	Tests 	Total Volume (mL) 
Screening	Hematology, chemistry/CK-MB  or Troponin I, coagulation, virus serology, immunology sample (AAV9/SMN Ab only), diagnostic confirmation sample	19.3-19.6
Day -1	Hematology, chemistry, coagulation, capillary blood gas	6.0
Day 2	Hematology, chemistry, coagulation, capillary blood gas	6.0
Day 7	Hematology, chemistry/CK-MB or Troponin I, coagulation, immunology sample	10.0-12.3
Day 14	Hematology, chemistry, coagulation immunology sample	9.0-11.0
Day 21	Hematology, chemistry, coagulation immunology sample	9.0-11.0
Day 30	Hematology, chemistry/CK-MB or Troponin I, coagulation, immunology sample	11.0-12.3
Day 44	Chemistry	1.3
Day 60	Hematology, chemistry/CK-MB or Troponin I, coagulation	6.0-6.3
Day 72	Chemistry	1.3

Visit	Tests 	Total Volume (mL) 
Month 3	Hematology, chemistry, coagulation	5
Month 4	Hematology, chemistry, coagulation	5
Month 5	Hematology, chemistry, coagulation	5
Month 6	Hematology, chemistry/CK-MB or Troponin I, coagulation	6.0-6.3
Month 7	Hematology, chemistry, coagulation	5
Month 8	Hematology, chemistry, coagulation	5
Month 9	Hematology, chemistry/CK-MB or Troponin I, coagulation	6.0-6.3
Month 10	Hematology, chemistry, coagulation	5
Month 11	Hematology, chemistry, coagulation	5
Month 12	Hematology, chemistry/CK-MB or Troponin I, coagulation	6.0-6.3
Last Study Visit (Month 15) 	Hematology, chemistry/CK-MB or Troponin I, coagulation	6.0-6.3
Total Volume for Study 1-Year Duration		137.9-147.3

Immunology = Serum antibody to AAV9 and SMN, IFN- $\gamma$  ELISpot to detect T-cell responses to AAV9 and SMN

 Immunology sample requires 4-6 mL of whole blood

 Maximum total blood volume specified for each visit; in cases where tests can be combined, lower blood volumes may be sufficient. Positive serology samples at screening and elevated T-cell responses at Day 30 may require additional surveillance samples not reflected in the table.

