## 1.1. Key Definitions

Term	Definition
AE	Adverse Event (AE): Any untoward medical occurrence in a clinical investigation patient which does not necessarily have a causal relationship with the drug or device under study.
Age	For a given event, age will be expressed in months and rounded to one decimal place. A month is standardized to a period of 30 days. Age at event = (date of event – date of birth +1) / 30.  Age at Baseline will be defined/displayed in months. Age at Baseline = (first dose date – date of birth +1)/30.
Baseline	Baseline, unless otherwise specified in the Statistical Analysis Plan (SAP) sections, refers to the last measurement or evaluation made prior to the injection of AVXS-101.
First Dose Date	The first dose date, study day 1, will be the date of administration of the first dose of study drug after enrollment.
MedDRA	Medical Dictionary for Regulatory Activities (MedDRA) is a medical terminology used to classify adverse event information associated with the use of biopharmaceuticals and other medical products.
Study Day	First dose of study medication will be administered on study day 1. There is no study day 0. If the event happened on or after the first dose date, study day is defined as event date – first dose date + 1. If the event happened prior to the first dose date, study day is defined as event date – first dose date.

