### 3.10. Study Flowchart and Schedule of Assessments

Figure 1: Study Design

 Four (4) week dosing between first three patients within each cohort to allow safety monitoring  
 Provided no dose related toxicities and DSMB determines acceptable to escalate/expand during quarterly meeting

Refer to Appendix 22.3 for the schedule of assessments.

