#### 6.5. Visit Windows

The time windows specified in Table 4.1 (Cohort 1 and 2) and Table 4.2 (Cohort 3) define how efficacy data will be assigned to protocol-specified time points. All time points and corresponding time windows are defined based on dosing date.

If more than one efficacy observation for a specific assessment is included in a time window, the assessment closer to the nominal time will be used. If there are two efficacy observations

equally distant to the nominal time, the latest one will be used in analyses. Any efficacy assessments occurring outside the analysis windows will be considered an assessment of an unscheduled visit.

**Table 4.1: Analysis Time Windows of Bayley Scales, HFMSE, Development Milestones and Pulmonary Exam – Cohort 1 and 2 Patients**

Scheduled Visit	Nominal Days (Study Day)	Acceptable Analysis Window in Study Days (Min Day – Max Day)
Baseline	-	< 1
Month 1	30	1 to 44
Month 2	60	45 to 74
Month 3	90	75 to 104
Month 4	120	105 to 134
Month 5	150	135 to 164
Month 6	180	165 to 194
Month 7	210	195 to 224
Month 8	240	225 to 254
Month 9	270	255 to 284
Month 10	300	285 to 314
Month 11	330	315 to 344
Month 12	360	≥345

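### The four-week minimum between Cohort 1 patients ends on study Day 29, so it does not secure the Day 30 review that Protocol 10.7 says it allows

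*Protocol*

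**What the plan says.** Protocol 10.7 sets a four-week interval between all Cohort 1 patients and gives its purpose: "to allow review of the safety analysis from six-time points (Days 1, 2, 7, 14, 21, 30) prior to dosing of the next patient".

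Elsewhere the interval is a minimum. Protocol 8 says: "Enrollment will be staggered with at least four weeks between patient injections for all patients in Cohort 1". Protocol 7.1 and SAP 3.5 agree.

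On day numbering, SAP 1.1 says: "First dose of study medication will be administered on study day 1. There is no study day 0". SAP 6.5 says of the efficacy visit windows: "All time points and corresponding time windows are defined based on dosing date". Its Table 4.1 places Month 1 at nominal study day 30.

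For the later cohorts the interval is repeated but the list of time points is not. Protocol 10.7 requires at least four weeks between the first three Cohort 2 patients. For Dose C it says: "there will again be a four-week interval between dosing of the first three patients receiving Dose C, as in Cohorts 1 and 2". A note to SAP Figure 1 (SAP 3.10) says: "Four (4) week dosing between first three patients within each cohort to allow safety monitoring". Neither text names Day 30.

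**The concern.** The interval is justified by a specific review that it is too short to guarantee. A site that doses the next child exactly four weeks after the last complies with the protocol, yet the last listed time point has not nominally occurred.

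Day 30 adds information. Protocol Table 7 gives the Day 7 and Day 30 blood samples as "Hematology, chemistry/CK-MB or Troponin I, coagulation, immunology sample". The Day 14 and Day 21 rows carry no cardiac marker. A decision taken on Day 29 would therefore rest on one post-dose CK-MB or troponin I sample instead of two. Protocol 5 describes this as the first clinical gene therapy trial of intrathecal delivery in SMA, so the spacing between the first patients is a real safeguard.

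**Working it through.** **Inputs**
- Minimum interval: 4 weeks = 28 days (Protocol 7.1, 8, 10.7).
- Time points to be reviewed: Days 1, 2, 7, 14, 21, 30 (Protocol 10.7).
- Study day = event date − dose date + 1 (SAP 1.1 and 6.2.2). The protocol's numbering agrees: in Protocol 12.8, 48 hours after dosing is Day 3, so dosing is Day 1.

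**The plan's figure.** Protocol 10.7 implies that four weeks covers 6 of 6 time points.

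**Check**
1. Study day of the earliest next dose = 28 + 1 = 29.
2. Time points before Day 29: 1, 2, 7, 14, 21. That is 5 of 6. Day 30 falls one day later.
3. If dosing were counted as Day 0 instead, the next dose would fall on Day 28. The count is again 5 of 6, with Day 30 two days later. The result does not depend on the numbering convention.

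**Interval needed.** A visit on Day v precedes the next dose only if that dose is on Day v + 1 or later, which is an interval of at least v days. For v = 30 this is 30 days, and 30 − 28 = 2 days above the minimum. Review time of r days comes on top; the documents do not state r.

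**Visit window (assumption).** The schedule of assessments shows windows of ±2 and ±7 days, but the table is broken in the text available and the columns covered by each cannot be read. The ranges would be:

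| Assumed window | Day 30 visit falls on | Interval needed | Above the 28-day minimum |
|---|---|---|---|
| none (nominal) | Day 30 | 30 days | 2 days |
| ±2 days | Days 28–32 | 28–32 days | 0–4 days |
| ±7 days | Days 23–37 | 23–37 days | 0–9 days |

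Under ±2, a visit held early on Day 28 would precede a Day 29 dose, with about one day left for results and review. The other four permitted days (29, 30, 31, 32) would not precede it. That is a count of allowed days, not a probability. The nominal result does not rest on either window.

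**Delay from closing the gap.** Three patients have two gaps: 2 × 2 = 4 days per cohort nominally, plus 2r days for review. Under ±2 the range is 2 × (0 to 4) = 0 to 8 days, plus 2r.

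**The case against.** The best defence reads the minimum and the purpose together: 28 days is the least allowed, Protocol 10.7 names Day 30 as something to be reviewed first, and a sponsor following that sentence would wait. On this view the text is loose by a day or two. The reading is fair and it limits the severity. It does not remove the point, because the purpose clause is not written as a condition for dosing and nothing else in the two documents supplies one. Protocol 7.5 says "An independent DSMB/DMC and medical monitor will monitor safety data on a continual basis throughout the trial", but that text, like Protocol 12.1.2, provides halts triggered by events, not a hold for scheduled data. The DSMB/DMC Charter, to which Protocol 15 refers the timing of reviews, is not available, so an operational hold there cannot be ruled out.

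A reader might infer more than the documents support:
- **That Cohorts 2 and 3 have the same shortfall.** The list of six time points is attached to Cohort 1 only. The later cohorts share the interval and a general monitoring purpose, so no stated promise is missed.
- **That the mouse heart and liver findings make the gap serious.** Those findings in Protocol 5.3 follow IV dosing. The same section reports less peripheral vector with CSF delivery, and Protocol 5.5 expects lower systemic exposure with intrathecal dosing.
- **That the one month of platelet monitoring in Protocol 5.5 bars earlier dosing of the next child.** It manages the treated patient's own risk and is not a criterion for the next dose.
- **That patients were dosed without Day 30 review.** The documents give no individual dosing dates.

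**Conclusion.** The point holds for Cohort 1. At the minimum interval, 5 of the 6 listed time points have nominally passed, and at least 30 days plus review time is needed for all six. This assumes that four weeks means 28 days, that the Day 30 visit is held on its nominal day, and that no hold exists in a document not seen here.

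The effect is minor. Hematology, chemistry and coagulation are also sampled on Days 7, 14 and 21. The sponsor confers with the DSMB/DMC on related Grade III or higher events before enrollment continues. What can be missed is mainly one visit and the second post-dose cardiac marker. Sample size, power and alpha are unaffected.

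**What to change.** In Protocol 10.7, make the interval at least four weeks, in line with Protocol 7.1 and 8, and add a condition such as: *The next Cohort 1 patient will not be dosed until the previous patient's Day 30 visit is complete and its available AE, examination, hematology, chemistry (including CK-MB or troponin I) and coagulation data have been reviewed.* ELISpot goes to the central laboratory (Protocol 12.14.7.3), so keep it outside the hold and review it when it arrives.

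Using the same condition for the first three patients of Cohorts 2 and 3 is sensible for consistency, since those intervals are introduced as a repeat of Cohort 1, but it would be a new requirement.

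The cost is about 2 days per gap nominally, or 4 days for a cohort of three, plus review time. No extra visits are needed. Protocol 12.14 allows local sampling when results are needed quickly; using it may mean some additional blood, so zero extra samples cannot be promised.

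SAP 2.2.1 records that the study was terminated early, so an amendment cannot change dosing already done. The sponsor can still report each actual interval and whether Day 30 data were reviewed before the next dose, and can correct the wording before it is reused.

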## **10.8. Study Product Accountability**

This is an open-label study. Eligible patients will be assigned a unique patient identification number once informed consent is obtained and all eligibility criteria are met.

The pharmacist or designee will maintain accurate records of the quantities of AVXS-101 received, dispensed, and destroyed. The pharmacist or designee will document the date and time of delivery of the dose vessel to the dose procedure room as well as the time the used vessel was prepared for destruction as per the Pharmacy Manual.

## **10.9. Study Product Handling and Disposal**

All materials used for injection, including sterile drapes, needles, and syringes in contact with the vector must be sealed in leak-proof containers. All waste must be sealed in bags bearing the biohazard symbol and disposed of in a biohazard waste container.

All transfers must be done in spill-proof containers. Individuals manipulating the vector will be required to wear PPE, such as gloves.

Any quality issue noticed with the receipt or use of AVXS-101 (e.g., deficiency in condition, appearance, pertaining to documentation, labeling, expiration date, etc.) should be promptly reported to AveXis in accord with procedures outlined in the Pharmacy Manual.

Under no circumstances will the Investigator supply AVXS-101 to a third party, allow AVXS-101 to be used other than as directed by this clinical trial protocol, or dispose of AVXS-101 in any other manner.

## 11. ASSESSMENT OF EFFICACY

### 11.1. Physical Assessments

#### 11.1.1. Hammersmith Functional Motor Scale- Expanded

The HFMSE was devised for use in children with SMA Type 2 and Type 3, to give objective information on motor ability and clinical progression.

The HFMSE will be administered by a qualified clinical evaluator (e.g., licensed physical or occupational therapist, or national equivalent) in accord with [Table 3](#) for all patients  $\geq$  24 months of age. Patients  $<$  24 months of age at time of dosing will begin having HFMSE assessments at such time that 24 months of age is reached.

The HFMSE sessions will be videotaped in accord with the AVXS-101-CL-102 Videotaping Manual.

#### 11.1.2. Bayley Scales of Infant and Toddler Development

Bayley Scales of Infant and Toddler Development© version 3 is a standardized, norm-referenced infant assessment and will be administered by a qualified clinical evaluator (e.g., licensed physical or occupational therapist, or national equivalent). The gross and fine motor subtests will be completed in accordance with [Table 3](#). See AVXS-101-CL-102 Physical Assessments Manual.

Bayley Scales assessments will be videotaped in accordance with the AVXS-101-CL-102 Videotaping Manual.

### 11.2. Motor Milestone Development Survey

The achievement of significant motor milestones will be assessed by the qualified clinical evaluator (e.g., licensed physical or occupational therapist, or national equivalent) using a standard Motor Milestone Development Survey shown in [Table 5](#) with definitions of each milestone driven by the Bayley Scales of Infant and Toddler Development (see AVXS-101-CL-102 Physical Assessments Manual). The clinical evaluator will record whether the patient has attained each of the milestones on the Motor Milestone Development Survey in accordance with [Table 3](#). Once observed, a motor milestone is considered attained. The date of attainment of each motor milestone will be determined by the date of the visit in which the milestone is observed.

During the screening visit, the clinical evaluator will complete an assessment of baseline milestone achievement in accordance with [Table 3](#); this assessment must be recorded on video and the findings must be documented in the source.

As the Bayley Scales do not necessarily require the child to repeat previously attained milestones, it is essential that each milestone be captured on video. Development milestone assessment sessions will be videotaped in accord with the AVXS-101-CL-102 Videotaping Manual.

**Table 5: Motor Milestone Development Survey**

Developmental Milestone- Bayley Scale Item Number	Performance Criteria
Head Control – Gross Motor Subtest Item #4	Child holds head erect for at least 3 seconds without support
Rolls from Back to Sides – Gross Motor Subtest Item #20	Child turns from back to both right and left sides
Sits Without Support – Gross Motor Subtest Item #26	Child sits alone without support for at least 30 seconds
Stands with Assistance - Gross Motor Subtest Item #33	Child supports own weight for at least 2 seconds
Crawls – Gross Motor Subtest Item #34	Child makes forward progress of at least 5 feet by crawling on hands and knees
Pulls to Stand – Gross Motor Subtest Item #35	Child raises self to standing position using chair or other convenient object for support
Walks with Assistance – Gross Motor Subtest Item #37	Child walks by making coordinated, alternated stepping movements
Stands Alone – Gross Motor Subtest Item #40	Child stands alone for at least 3 seconds after you release his or her hands
Walks Alone – Gross Motor Subtest Item #43	Child takes at least five steps independently, displaying coordination and balance

